9.5.2 Analyses of Secondary Efficacy Endpoint(s)

The secondary efficacy endpoints calculated by the methods as specified detailed in [Table 9-2](#). Secondary Efficacy Endpoint Summary Table, column Primary Summary and Analysis Method.

For continuous secondary endpoints, a generalized linear mixed effects model with the identity link function will be used. The model will include the corresponding baseline value for the endpoint being analyzed, visit, the prevailing erenumab dose from Week 12 onwards, and baseline MMD. The corresponding 95% CI will be estimated from the LSM of the mixed effects model, and p-values comparing with zero at a two-sided 5% significance level will be reported.

For binary secondary endpoints, a generalized linear mixed effects model with the logit link function will be used. The model will include the corresponding baseline value for the endpoint being analyzed (except for the global impression endpoints), visit, the prevailing erenumab dose from Week 12 onwards, and baseline MMD. The proportions and the corresponding 95% CI will be estimated from the LSM (with inverse link function) of the mixed effects model and will be reported.

The secondary endpoints will be analyzed in the following subgroups:

- Whether remained on standard of care migraine preventive treatment throughout the study (yes vs. no)
- Migraine type (EM vs. CM)

The subgroups will be re-examined for appropriateness and may be re-categorized (due to small sample size, for example, if there are < 10% of subjects within a subgroup) before final analysis.

The purpose of the subgroup analyses is to explore if the treatment effect varies across subgroups of interest. Subgroup analyses will be performed using the same method as primary analysis method but within level of each subgroup of interest.

The efficacy analysis set will be used for this endpoints analyses.

9.5.3 Analyses of Exploratory Efficacy Endpoint(s)

The exploratory efficacy endpoints calculated by the method as specified in [Table 9-3](#). All the exploratory endpoints will be analyzed the same way as that for the primary and secondary endpoints **without any intercurrent event handling**.

The subgroup analysis is not applicable for exploratory endpoints.

The efficacy analysis set will be used for all the exploratory endpoint analyses.

9.6 Safety Analyses

All safety analyses will be performed based on all subjects in the Safety Analysis Set, both overall and separately by migraine prevention therapy standard of care status (continuation vs discontinuation).

The safety analysis will includes the adverse events, serious adverse events, and adverse device effects.

No formal hypothesis testing will be performed for this study.

9.6.1 Adverse Events

The Medical Dictionary for Regulatory Activities (MedDRA) version **26.0** or later will be used to code all adverse events.

Subject incidence of all treatment-emergent adverse events will be tabulated by system organ class (SOC) and preferred term (PT). Tables of fatal adverse events, serious adverse events, adverse events leading to discontinuation from investigational product or other protocol-required therapies, and adverse events of interest (EOI) including:

- **Ischaemic Central Nervous System Vascular Conditions SMQ (Narrow)**
- **Ischaemic Heart Disease SMQ (Narrow and Broad)**
- **Peripheral Arterial Disease AMQ (Narrow)**
- **Hypertension SMQ (Narrow and Broad)**
- **Constipation AMQ (Narrow and Broad)**
- **Alopecias AMQ (Broad)**
- **COVID-19 SMQ (Narrow)**

Subject incidence of device-related events, if applicable, will be tabulated by system organ class and preferred term.

In addition, summaries of treatment-emergent and serious adverse events will be tabulated by SOC, PT, and grade.

The adverse event grading scale to be used for this study will be the Common Terminology Criteria for Adverse Events (CTCAE) version 4.03.

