1.3 Schedule of Activities (SoA)

Table 1-1. Subject Study Visits Through Open-label Treatment Phase

PROCEDURE	Screening (up to 3 weeks before baseline) ^c	Baseline (4-5 weeks before day 1) ^c	Open-label Treatment Period (24 weeks)							Notes
			Day 1 ^e	Week 4	Week 8	Week 12	Week 16	Week 20	Week 24/ EOS	
GENERAL ASSESSMENTS										
Informed consent	X									
Inclusion and exclusion criteria	X									
Demographics	X									
Medical history	X									
Neurological medical history	X									
Gastrointestinal medical history	X									
Headache and migraine frequency medical history	X									
Migraine preventive medications review	X	X	X	X	X	X	X	X	X	At screening, a review of the subject's history of migraine preventive use (past and current) will be conducted. At subsequent visits, information will be collected regarding concomitant standard of care preventive status (ie, whether still taking and at what dose).
Prior therapies review	X									Includes all prior medications (other than prior migraine preventive medications) that were being taken/used within 120 days prior to screening through the signing of the informed consent.
Concomitant therapies review	X	X	X	X	X	X	X	X	X	
Eligibility criteria after baseline period			X							Compliance with eDiary usage will be assessed on day 1 to determine eligibility before any other day 1 assessments.
Physical measurements			X							Height/weight for BMI

Footnotes are defined on the last page of this table.

Page 1 of 3

Table 1-1. Subject Study Visits Through Open-Label Treatment Phase

PROCEDURE	Screening (up to 3 weeks before baseline) ^c	Baseline (4-5 weeks before day 1) ^c	Open-label Treatment Period (24 weeks)							Notes
			Day 1 ^e	Week 4	Week 8	Week 12	Week 16	Week 20	Week 24/ EOS	
SAFETY ASSESSMENTS										
Adverse events			X	X	X	X	X	X	X	
Serious adverse events	X	X	X	X	X	X	X	X	X	
Adverse device effects			X	X	X	X	X	X		
Product complaints			X	X	X	X	X	X		
LABORATORY ASSESSMENTS										
Urine pregnancy test (females of childbearing potential only)	X		X			X			X	Additional on-treatment pregnancy testing may be performed at the investigator's discretion if there is suspicion that a female subject is pregnant or per local laws and regulations.
CLINICAL OUTCOME ASSESSMENTS										
eDiary		Daily				Daily				
ETS			X							
GAD-7			X			X			X	
MFIQ			X			X	X	X	X	
mGI-I						X	X	X	X	To be completed by subject and clinician
MIBS-4			X			X	X	X	X	
MSSS			X			X	X	X	X	
PHQ-9	X ^d		X			X			X	

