2.3 Benefit/Risk Assessment

Benefits

Globally, the totality of data from phase 2 and phase 3 studies in subjects with CM and EM provides substantial evidence for the efficacy and safety of erenumab in adults with migraine. The key benefits of erenumab include reduction in MMD, reduction in acute migraine-specific medication use, as well as improvements in a range of other patient-reported outcomes (PROs), favorable tolerability, low treatment discontinuation rates, convenience (Q4W injections with the option of self-administration), and rapid onset of effect.

Risks

The safety profile of erenumab has been favorable in clinical trials and in the post-marketing setting. A limited number of adverse drug reactions (injection site reactions, constipation, muscle spasm, and pruritus) have been identified at low frequencies (< 5%) in clinical trials. In the long-term use of erenumab, the safety profile remained consistent through 5 years of open-label treatment. In post-marketing settings, **hypertension**, hypersensitivity reactions (including rash, angioedema and anaphylactoid reactions), and constipation with serious complications have been reported. In addition, oral sores (eg, stomatitis, mouth ulceration, oral mucosal blistering), alopecia and rash (eg, rash papular, exfoliative rash, rash erythematous, urticaria, blister) have been observed in post-marketing surveillance.

The above benefit risk assessment supports the conduct of this clinical trial. Reference should be made to the currently approved Investigator's Brochure and Prescribing Information, where Aimovig® is approved, for further data on erenumab.

3. Objectives and Endpoints/Estimands

Objectives	Endpoints
Primary	

 To evaluate the effect of erenumab on medication-specific treatment satisfaction 	
 Change from baseline in the Treatment Satisfaction Questionnaire for Medication (TSQM) overall satisfaction scale score at week 24, as measured by items 12 to 14 of the TSQM version 1.4
Primary Estimand	

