 - Tricyclic antidepressants (eg, amitriptyline, nortriptyline, protriptyline)
 - Duloxetine, milnacipran
 - Verapamil
 - Lisinopril, candesartan
 - Clonidine, guanfacine
 - Cyproheptadine
 - **OnabotulinumtoxinA (subjects using concomitant onabotulinumtoxinA for migraine prevention are allowed [but not required] to also take one oral preventive migraine medication)**

During the baseline period:

- 108 Must have ≥ 4 MMD based on the eDiary data during the last 28 days of the baseline (if longer than 28 days)
- 110 Must have demonstrated $\geq 75\%$ compliance with the eDiary, based on the last 28 days of the baseline period (if longer than 28 days)

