8.2.4 Physical Measurements

The subject's height (in centimeters) should be measured without shoes. Weight (in kilograms) should be measured without shoes.

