8.4.1 Clinical Laboratory Assessments

Refer to [Section 11.2](#) for the list of clinical laboratory tests to be performed and to the Schedule of Activities ([Table 1-1](#)) for the timing and frequency.

All protocol-required laboratory assessments, as defined in [Section 11.2](#), must be conducted in accordance with the laboratory manual and the Schedule of Activities ([Table 1-1](#)). Note: the only protocol-required laboratory assessment is the urine pregnancy test for women of childbearing potential.

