8.4.2.2 Method of Detecting Adverse Events and Serious Adverse Events

Care will be taken not to introduce bias when detecting adverse events and/or serious adverse events. Open-ended and non-leading verbal questioning of the subject is the preferred method to inquire about adverse event occurrence.

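### Hypertension is an event of interest, but no blood pressure is scheduled and the planned safety tables cannot separate erenumab from withdrawal of a blood-pressure-lowering preventive

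*SAP*

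**What the plan says.** Protocol 2.3 includes hypertension in its list of post-marketing reports: "In post-marketing settings, hypertension, hypersensitivity reactions". SAP 9.6.1 lists "Hypertension SMQ (Narrow and Broad" as one of seven event-of-interest groups. The SAP change log explains that new events of interest were added because they are summarised across other studies of the product.

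Table 1-1 of the protocol has no blood pressure or vital-signs row. Its physical measurements row is a single day 1 entry, "Height/weight for BMI", and Section 8.2.4 covers only height and weight ("Weight (in kilograms) should be measured without shoes"). Section 8.4.1 notes that "the only protocol-required laboratory assessment is the urine pregnancy test for women of childbearing potential". For adverse events generally, Section 8.4.2.2 says: "Open-ended and non-leading verbal questioning of the subject is the preferred method to inquire about adverse event occurrence".

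Inclusion criterion 107 requires one migraine preventive at entry. Permitted drugs include beta blockers, verapamil, "Lisinopril, candesartan", clonidine and guanfacine, alongside drugs such as topiramate and tricyclic antidepressants. The synopsis (Treatments) and Section 6.7.1 let subjects stay on the preventive or stop it fully. The synopsis and SAP 3.1 also allow dose changes, to be finished by week 12.

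SAP 9.6 reports all safety analyses "both overall and separately by migraine prevention therapy standard of care status (continuation vs discontinuation". Neither document splits them by preventive class or by whether an event came before or after the preventive was changed.

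**The concern.** Two things limit what the hypertension table can show, and they pull in opposite directions.

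The first is ascertainment. With no scheduled reading there is no systematic baseline or follow-up value, and detection depends on what subjects report or investigators happen to observe. Between day 1 and week 12, when preventives are being stopped, the required contacts at weeks 4 and 8 are telephone visits. A low count could be taken as reassurance that it does not give.

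The second is mixing of causes. A rise in blood pressure after a subject stops, say, a beta blocker would, if reported, be a treatment-emergent event, because SAP 5.1.3 defines these by timing. It would sit in the discontinuation column beside subjects who stopped topiramate. A difference between the two columns could then be misread as a feature of using erenumab without background treatment. This does not depend on how standard-of-care status is assigned: perfect assignment would leave it in place.

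Because the same events of interest are summarised across the programme, the figure is likely to be set beside figures from other studies.

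**Working it through.** **The plan's own figures.** The documents give no figure for hypertension. Their precision tables (Protocol Table 9-1, SAP Tables 3-1 and 3-2) concern the binary efficacy endpoints. They reproduce, for example 1.96 × √(0.5 × 0.5 / 216) = 6.7%, but they do not bear on this point.

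**Inputs.** From the documents: n = 240 enrolled (SAP 3.2). Everything else is assumed, because the documents give no shares or event rates:
- e, background rate of recorded hypertension events: 1%
- b, share on a blood-pressure-lowering preventive: 35%, range 20% to 50%
- q, share stopping their preventive, taken as equal across classes: 50%
- w, extra recorded events among those who stop such a drug: 5 to 10 percentage points

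The erenumab effect is the same in every subject, so any column difference comes from withdrawal alone.

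**Formulas.** Continuation column = e. Discontinuation column = e + b·w. Overall = e + b·q·w.

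**Central case, b = 35%.**
- Subjects stopping such a drug: 240 × 0.35 × 0.5 = 42
- Extra events: 42 × 0.05 = 2.1 to 42 × 0.10 = 4.2
- Overall: (2.4 + 2.1)/240 = 1.9% to (2.4 + 4.2)/240 = 2.8%
- Discontinuation column: (1.2 + 2.1)/120 = 2.8% to (1.2 + 4.2)/120 = 4.5%
- Continuation column: 1.0%

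**Range of b.** Discontinuation column from 1% + 0.20 × 5% = 2.0% to 1% + 0.50 × 10% = 6.0%, against 1.0%.

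**Other assumptions.** With e = 2%, b = 10% to 50%, q = 20% to 50% and w = 5 to 10 points, the discontinuation column is 2.5% to 7.0% against 2.0%, and the overall figure is 2.1% to 4.5%. With w = 0 the distortion is zero in every case.

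**Under-ascertainment.** If the true incidence is 1% to 5% and 25% to 100% of cases are reported (both assumed), the table shows 1% × 0.25 = 0.25% up to 5% × 1.00 = 5.0%. A count of 0/240 has an exact two-sided 95% upper limit of 1 − 0.025^(1/240) = 1.5%, which bounds the true incidence only if detection is complete.

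**The case against.** The strongest reply is that the SAP promises little and delivers it. It tabulates subject incidence of reported treatment-emergent events, calls all analyses descriptive for want of a control arm (SAP 9.1) and plans no formal testing (SAP 9.6). Treatment-related events are defined separately (SAP 5.1.3), and Protocol Appendix 11.4 has investigators weigh concomitant therapy and timing when judging causality. The event-of-interest list is a programme-wide convention, not a promise to monitor blood pressure. Any second drug from the preventive classes taken for another indication must be expected to stay stable (Protocol 6.1.7), which narrows the scope for withdrawal. Every input above except n is assumed, and inflation needs withdrawal events to be recorded while the ascertainment argument says events are missed, so the net direction is unknown.

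Much of this stands, and it rules out four stronger readings that a reader might draw:

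- *Blood pressure is never measured.* The documents show only that it is not scheduled. Investigator-observed events are reportable (Protocol 8.4.2.1.1), and Appendix 11.4 counts a clinically significant vital-sign finding as an adverse event. A reading taken at an onsite visit could therefore enter the data.
- *The tables cannot support an incidence.* They support a crude incidence of reported events. They do not support a complete or measured one.
- *Every column mixes withdrawal with erenumab.* The continuation column excludes full withdrawal; only dose changes can enter it.
- *The plan presents withdrawal effects as an erenumab harm.* It makes no attribution claim.

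The reply does not answer the layout. A descriptive table still needs a label that says how events were found. Causality judgements do not help if the event-of-interest table is not restricted to, or shown with, them. The factors listed in SAP 8.4 as possible sources of bias do not include changes to the preventive.

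**Conclusion.** The point holds in a limited form. The planned table gives a crude, possibly under-ascertained incidence of reported hypertension, and its overall and discontinuation columns cannot separate erenumab from withdrawal of a blood-pressure-lowering preventive. The discontinuation column also pools all preventive classes and, with no timing rule, may include events that began before the preventive was stopped.

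The size of the distortion cannot be found from the documents. The 2% to 6% against 1% rests on an assumed background rate, assumed drug shares, equal stopping across classes and an assumed withdrawal excess. Under-reporting could offset some or all of it. No primary or secondary endpoint and no sample-size figure is affected. This is a worthwhile, inexpensive improvement to safety reporting, not a flaw in the efficacy analysis.

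**What to change.** In SAP 9.6.1:

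1. Tabulate the hypertension event of interest by class of entry preventive (blood-pressure-lowering versus other, with the drugs in each class listed in the SAP) and by preventive status (stopped, dose changed, unchanged). State how subjects on onabotulinumtoxinA plus one oral preventive are classed.
2. Add a subject-level listing of each event: the preventive, the date or visit interval of any stop or dose change, the onset date and the investigator's causality assessment.
3. Label the table *Reported hypertension events (blood pressure not scheduled by protocol)* and state the ascertainment limit in the study report.
4. Show subjects with an unchanged preventive beside the full table, as supportive only, because that group is defined after baseline.

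The cost is SAP wording, one table and one listing. Preventive status and dose are reviewed at every visit (Table 1-1), and a summary by medication category is already planned (SAP 9.6.4). If exact stop dates were not collected, the visit data place each change between two visits. The downside is small cells: the central case gives 2.4 + 2.1 = 4.5 to 2.4 + 4.2 = 6.6 events over six cells, so the listing will carry most of the information. The analysis cannot recover blood pressure values that were not taken. No change to clinical monitoring or to the management of preventives is proposed.

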9.6.2 Laboratory Test Results

Not applicable.

9.6.3 Exposure to Investigational Product

The number and percentage of subjects with dose change, reason for dose change for **both dose adjustment and none or partial dose**, and duration of exposure to investigational product in days will be summarized over time.

Descriptive statistics will be produced to describe the exposure to investigational product by migraine types (EM/CM) separately and overall population.

9.6.4 Exposure to Concomitant Medication

Number and proportion of subjects receiving migraine preventive medications will be summarized by medication category. Number and proportion of subjects who discontinue standard of care migraine prevention therapy will also be summarized.

9.7 Other Analyses

Not applicable.

10. Changes From Protocol-specified Analyses

Frequency of headache and migraine days collected on CRF “Headache and Migraine Frequency Medical History” at screening period will be included to derive migraine type, in addition to eDiary at baseline.

The definition of efficacy analysis set stated in the protocol is not applicable to all efficacy endpoints and has been corrected in Section 6.3 to what was intended. These changes will also be documented in the clinical study report.

11. Literature Citations / References

NA

12. Prioritization of Analyses

Prioritization of analyses has not been identified at this time.

13. Data Not Covered by This Plan

There are no plans to specifically analyze or summarize the following substudy outcome variables.

- Migraine impact
- Treatment efficacy
- Migraine experience

Qualitative data on changes resulting from treatment received in the open-label treatment period will be collected via telephone interview.

Data will be analyzed to achieve the study objectives, using qualitative data analysis software (ie, ATLAS.ti).

14. Appendices

Not applicable.
